5.2.3 Dose Modification Protocol

- Held doses of either drug will be considered as omitted. (For example, if temsirolimus is held on cycle 2, day 8, the next dose of temsirolimus the following week will be considered cycle 2, day 15, rather than delaying the cycle and repeating the day 8 dose.)
- Laboratory values should be rounded to one significant digit.
- For any toxicity (regardless of grade), despite optimal supportive care, that is felt by the treating investigator to represent a risk to the patient's safety, additional dose reduction,

treatment delay, or treatment discontinuation is permitted at the discretion of the treating investigator.

Toxicity	Grade (NCI CTCAE v4.0)	Temsirolimus Adjustment	Sorafenib Adjustment
HEMATOLOGIC			
Neutropenia	Grade 1 (ANC 1500 to < 2000/mm ³)	No change	No change
	Grade 2 (ANC 1000 to < 1500/mm ³)	No change	No change
	Grade 3 (ANC 500 to < 1000/mm ³)	Hold both drugs and recheck weekly until ≤ Grade 2, then decrease TEM by 1 DL and continue SOR at same dose; if recurs, hold both drugs and recheck weekly until ≤ Grade 2, then decrease SOR by 1 DL and continue TEM at same dose; continue alternating dose reductions if toxicity recurs	
	Grade 4 (ANC < 500/mm ³)	Hold both drugs and recheck weekly until ≤ Grade 2, then decrease both drugs by 1 DL	
Lymphopenia	Any Grade	No dose reductions or delays will be performed for lymphopenia	
Thrombocytopenia	Grade 1 (PLT 75,000 to < LLN/mm ³)	No change	No change
	Grade 2 (PLT 50,000 to < 75,000/mm ³)	No change	No change
	Grade 3 (PLT 25,000 to < 50,000/mm ³)	Hold both drugs and recheck weekly until ≤ Grade 2, then decrease TEM by 1 DL and continue SOR at same dose; if recurs, hold both drugs and recheck weekly until ≤ Grade 2, then decrease SOR by 1 DL and continue TEM at same dose; continue alternating dose reductions if toxicity recurs	
	Grade 4 (PLT < 25,000/mm ³)	Hold both drugs and recheck weekly until ≤ Grade 2, then decrease both drugs by 1 DL	
Anemia	Any Grade	No dose reductions or delays will be performed for anemia; transfusions and/or growth factor support may be used at the discretion of the investigator	
GASTROINTESTINAL (EXCLUDING HEPATIC DYSFUNCTION)			
Nausea/vomiting, constipation, or mucositis (despite optimal supportive care)	Grade 1	No change	No change
	Grade 2	No change	No change

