	Grade 3	Hold both drugs until ≤ Grade 2, then decrease TEM by 1 DL and continue SOR at same dose; if recurs, hold both drugs until ≤ Grade 2, then decrease SOR by 1 DL and continue TEM at same dose; continue alternating dose reductions if toxicity recurs	
	Grade 4	Hold both drugs until ≤ Grade 2, then decrease both drugs by 1 DL	
Diarrhea (despite optimal supportive care)	Grade 1	No change	No change
	Grade 2	No change	No change
	Grade 3	Hold both drugs until ≤ Grade 2, then decrease SOR by 1 DL and continue TEM at same dose; if recurs, hold both drugs until ≤ Grade 2, then decrease TEM by 1 DL and continue SOR at same dose; continue alternating dose reductions if toxicity recurs	
	Grade 4	Hold both drugs until ≤ Grade 2, then decrease both drugs by 1 DL	

Toxicity	Grade (NCI CTCAE v4.0)	Temsirolimus Adjustment	Sorafenib Adjustment
HEPATIC DYSFUNCTION			
Hyperbilirubinemia (substitute direct bilirubin values and normal ranges for patients with Gilbert's Syndrome)	Grade 1 (BILT > ULN to 1.5 times ULN)	No change	No change
	Grade 2 (BILT > 1.5 to 3 times ULN)	Hold both drugs and recheck weekly until ≤ Grade 1, then decrease SOR by 1 DL and continue TEM at same dose; if recurs, hold both drugs and recheck weekly until ≤ Grade 2, then decrease TEM by 1 DL and continue SOR at same dose; continue alternating dose reductions if toxicity recurs	
	Grade 3 (BILT > 3 to 10 times ULN)	Hold both drugs and recheck weekly until ≤ Grade 1, then decrease both drugs by 1 DL	
	Grade 4 (BILT > 10 times ULN)	Discontinue protocol therapy	
Transaminase and alkaline phosphatase elevation (if assessed as treatment-related, clinically relevant, and ≥ 2 grades from baseline)	Grade 1 (> ULN to 2.5 times ULN)	No change	No change
	Grade 2 (> 2.5 to 5 times ULN)	No change	No change
	Grade 3 (> 5 to 20 times ULN)	Hold both drugs and recheck weekly until ≤ Grade 2, then decrease SOR by 1 DL and continue TEM at same dose; if recurs, hold both drugs and recheck weekly until ≤ Grade 2, then decrease TEM by 1 DL and continue SOR at same dose; continue alternating dose reductions if toxicity recurs	
	Grade 4 (> 20 times ULN)	Discontinue protocol therapy	
Ascites	Grade 1 (Asymptomatic)	No change	No change

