Arterial thrombosis, including myocardial ischemia or infarction, cerebrovascular accident, or mesenteric ischemia	Any Grade	Discontinue protocol therapy	
Venous thrombo-embolism* requiring anticoagulation (*excluding portal or hepatic vessel thrombosis or tumor thrombus)	Any Grade	Discontinue protocol therapy	
RENAL AND METABOLIC			
Elevated creatinine (despite optimal supportive care, i.e. hydration if dehydrated, and if assessed as treatment-related, clinically relevant, and ≥ 1 grade from baseline)	Grade 1 (CRE > ULN to 1.5 times ULN)	No change	No change
	Grade 2 (CRE > 1.5 to 3 times ULN)	Hold both drugs and recheck weekly until ≤ Grade 1, then resume at prior doses; if recurs, hold both drugs and recheck weekly until ≤ Grade 1, then decrease TEM by 1 DL and continue SOR at same dose; if recurs again, hold both drugs and recheck weekly until ≤ Grade 1, then decrease SOR by 1 DL and continue TEM at same dose; continue alternating dose reductions if toxicity recurs	
	Grade 3 (CRE > 3 to 6 times ULN)	Hold both drugs and recheck weekly until ≤ Grade 1, then decrease both drugs by 1 DL	
	Grade 4 (CRE > 6 times ULN)	Discontinue protocol therapy	
Hypo-phosphatemia	Grade 1	No change	No change
	Grade 2	No change	No change

Toxicity	Grade (NCI CTCAE v4.0)	Temsirolimus Adjustment	Sorafenib Adjustment

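### Section 5.2.3 rounds laboratory values to one significant digit, which moves some Grade 3 platelet and neutrophil counts into the no-change row of its own dose table

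*Combined protocol and SAP*

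**What the plan says.** Section 5.2.3 opens with general rules for dose modification. One reads: "Laboratory values should be rounded to one significant digit". The next rule lets the investigator reduce, delay or stop treatment for a toxicity of any grade thought to endanger the patient. The grade-by-grade table then follows.

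The rows that matter most are given per mm³:

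- Neutropenia: "Grade 1 (ANC 1500 to < 2000", then Grade 2 from 1,000 to below 1,500, then "Grade 3 (ANC 500 to < 1000", then "Grade 4 (ANC < 500".
- Thrombocytopenia: Grade 2 from 50,000 to below 75,000, then "Grade 3 (PLT 25,000 to < 50,000", then Grade 4 below 25,000.

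In both rows Grade 2 means no change to either drug. Grade 3 means holding both drugs until recovery to Grade 2 or better, then lowering one of them. Grade 4 means the same hold, then lowering both.

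Three other rows use multiples of ULN, and their Grade 4 entries require protocol therapy to stop: "Grade 4 (BILT > 10 times ULN" for bilirubin, "Grade 4 (> 20 times ULN" for transaminases and "Grade 4 (CRE > 6 times ULN" for creatinine.

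**The concern.** Rounding to one significant digit is coarser than the table. Cut-points of 1,500, 25,000 and 75,000/mm³ and of 1.5 and 2.5 times ULN cannot be written with one digit, and no one-digit value lies in the Grade 1 neutropenia row. The rule and the table were evidently not written to work together.

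The practical problem is at the cut-points that decide dosing. A site that follows the text could continue or restart both drugs, or reduce one instead of two, where the reported value calls for the stricter action. A rounded count would also pass as recovered during a hold. Two sites reading the sentence differently could dose the same count differently. Section 8.2 grades adverse events by CTCAE v4.0 with no rounding, so one platelet count could be recorded as Grade 3 and dosed as Grade 2. The frequencies of dose reduction, delay and discontinuation are secondary tolerability measures (Sections 2.4.2 and 9.1.3) and would be affected.

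**Working it through.** The plan gives no figure to reproduce. The check is to grade each value as reported, round it, and grade it again.

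**Rule.** For a value x, let k be the integer part of log₁₀(x), rounded down. The rounded value is 10ᵏ × round(x / 10ᵏ), with halves rounded up.

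- Platelets 47,000: k = 4, 4.7 rounds to 5, giving 50,000.
- ANC 970: k = 2, 9.7 rounds to 10, giving 1,000.
- ANC 480: k = 2, 4.8 rounds to 5, giving 500.

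**Counts.** Cut-points are from Section 5.2.3. For platelets, the results cover Grades 2 to 4.

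| Reported value (/mm³) | Rounded | Grade as reported | Grade after rounding | Change in action |
|---|---|---|---|---|
| Platelets 45,000–49,999 | 50,000 | 3 | 2 | hold and reduce one → no change |
| ANC 950–999 | 1,000 | 3 | 2 | hold and reduce one → no change |
| ANC 450–499 | 500 | 4 | 3 | reduce both → reduce one |
| ANC 1,500–1,999 | 2,000 | 1 | 0 | none |

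If halves are rounded to even, the bands become platelets 45,001–49,999 and ANC 451–499. ANC 950–999 is unchanged, and a platelet count of exactly 25,000 goes from Grade 3 to 4. The tie rule is not material.

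**Share of the grade range (not of patients).**

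- Grade 3 platelets: (50,000 − 45,000) / (50,000 − 25,000) = 5,000 / 25,000 = 20%.
- Grade 3 ANC: (1,000 − 950) / (1,000 − 500) = 50 / 500 = 10%.
- Grade 4 ANC: (500 − 450) / 500 = 10%.

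**Tests graded by multiples of ULN, if the multiple is rounded.** Bilirubin 10.01–14.99×, transaminases 20.01–24.99× and creatinine 6.01–6.49× go from Grade 4 to Grade 3. Bilirubin 3.01–3.49×, transaminases 5.01–5.49× and creatinine 3.01–3.49× go from Grade 3 to Grade 2.

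**The same tests, if the raw value is rounded.** The result depends on the local ULN, which the documents do not give, so the ULNs below are assumptions.

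| Test, assumed ULN | Moves to a laxer grade | Moves to a stricter grade |
|---|---|---|
| AST, 40 | 201–249 (3→2), 801–849 (4→3) | none that alters dosing |
| AST, 35 | 701–749 (4→3) | 150–175 (2→3) |
| Creatinine, 1.2 | 7.21–7.49 (4→3) | 1.50–1.80 (1→2), 3.50–3.60 (2→3) |
| Creatinine, 1.3 | none loses Grade 4 | 1.50–1.95 (1→2), 3.50–3.90 (2→3), 7.50–7.80 (3→4) |
| Bilirubin, 1.0 | 3.1–3.4 (3→2), 10.1–14.9 (4→3) | 1.5 (1→2) |
| Bilirubin, 1.2 | 12.1–14.9 (4→3) | 1.5–1.8 (1→2), 3.5–3.6 (2→3) |

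These rows therefore have no single direction.

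**Does Section 5.3 make this moot?** For asymptomatic laboratory changes, that section requires modification only if the change is treatment-related, clinically relevant and at least two grades from baseline. Using the entry limits in Section 3.3.1:

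- Platelets at entry are at least 75,000 (Grade 0 or 1), so a true Grade 3 is at least two grades worse. That condition is met and the required hold is lost by rounding.
- With entry ANC of 1,000–1,499 (Grade 2), a value of 950–999 is one grade worse, so no action is lost.
- With the same entry ANC, a value of 450–499 is two grades worse as reported (4 − 2 = 2) but one after rounding (3 − 2 = 1). An asymptomatic patient then needs no modification at all.
- Patients entering with transaminases above 2.5 times ULN are already Grade 2, so Grade 3 triggers no hold, rounded or not.

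**The case against.** The strongest reply is that one decimal place was meant. That is plausible, since several chemistry limits in the protocol are written that way. Counts per mm³ would then be unaffected, and ULN multiples would be misgraded only within about 0.04 above a limit (for example 10.01–10.04 times ULN for bilirubin). But the text does not say this. If a laboratory reports ANC in thousands (an assumption), 0.45–0.49 and 0.95–0.99 would still drop a grade.

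The second reply is that patients are protected in other ways. The discretion rule beside the rounding sentence applies whatever the grade. Section 5.2.4 removes patients for any toxicity the investigator finds unacceptable, and its list is open-ended. Blood counts and chemistry are repeated weekly. All this limits the harm. However, the discretion rule permits a hold where the table requires one. The listed criteria in 5.2.4 for serious, life-threatening or irreversible toxicity refer to Grades 3 and 4, and the section does not say whether a rounded grade carries over.

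It is also fair that the platelet and ANC errors arise at 50,000, 1,000 and 500, which are one-digit numbers, and that the unreachable Grade 1 neutropenia row changes no dose. The two-digit cut-points show that the rule does not fit the table; they do not cause those errors.

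**Conclusion.** The concern holds. Read as written, the rule doses platelets of 45,000–49,999 and ANC of 950–999 as Grade 2 instead of Grade 3, and ANC of 450–499 as Grade 3 instead of Grade 4. These results assume only the stated rule and ordinary rounding. The shifts for bilirubin, transaminases and creatinine also depend on what is rounded and on the local ULN, and some are to a stricter grade.

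How many patients this would touch cannot be derived, because no distribution of values is given. The platelet row is likely to be used: Section 1.2.3.1 reports treatment-related thrombocytopenia of Grade 3 or higher in 24% of the phase I patients. That was a dose-finding trial graded by CTCAE v3.0, and the figure includes Grade 4. Neutropenia is not among the most common events listed there.

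This is a fault in a dosing instruction. It bears on patient safety near the cut-points, on consistency between sites and on the tolerability frequencies. No effect on TTP, power or the safety stopping rule is shown. It should be corrected.

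**What to change.** Delete the rounding sentence from Section 5.2.3, or replace it with: *Grade and dose-modify on the laboratory value as reported, without rounding.* Every band above then takes the action the table assigns to the reported value. The cost is one sentence in a protocol amendment.

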Clearance of the mTOR inhibitor everolimus in patients with hepatic dysfunction is markedly reduced, leading to the recommendation that everolimus dosage should be reduced in the setting of impaired hepatic function.(Dancey 2006) A pharmacokinetic and pharmacodynamic study of temsirolimus in patients with advanced malignancies and varying degrees of liver dysfunction showed no significant difference in temsirolimus exposure in patients with mild to moderate liver dysfunction; in patients with Child-Pugh score of C, however, exposure to temsirolimus and its metabolite was increased.(Pfizer 2011) This study was conducted by the National Cancer Institute (NCI) Organ Dysfunction Working Group (ODWG) and was presented at the American Society of Clinical Oncology Annual Meeting in 2011.(Sarantopoulos 2011) The authors demonstrated decreased clearance, prolonged half-life, and increased AUC in patients with greater degrees of hepatic dysfunction. According to Prescribing Information, a reduction in temsirolimus starting dose to 15 mg weekly is recommended in patients with mild to moderate liver dysfunction as defined by bilirubin > 1 to 1.5 times ULN and/or AST > ULN but bilirubin within normal limits, and temsirolimus is contraindicated in patients with total bilirubin greater than 1.5 times the upper limit of normal.(Wyeth 2011)

Strong inducers of CYP3A4/5 may decrease exposure to temsirolimus and sirolimus and should be avoided. Strong inhibitors of CYP3A4 may increase exposures and should be avoided.

Moderate CYP3A4 inhibitors should be used with caution or substituted with an alternate agent. Other agents and classes with potential for drug interactions with temsirolimus are reviewed in *Section 6.7 and Appendices 6-9 Prohibited Medications*.

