Elimination is primarily via the feces. After a single IV dose of [14C]-temsirolimus approximately 82% of total radioactivity was eliminated within 14 days, with 4.6% and 78% of the administered radioactivity recovered in the urine and feces, respectively. Following a single 25 mg dose of TORISEL® in patients with cancer, temsirolimus mean (CV) systemic clearance was 16.2 (22%) L/h. Temsirolimus exhibits a bi-exponential decline in whole blood concentrations and the mean half-lives of temsirolimus and sirolimus were 17.3 hr and 54.6 hr.

Temsirolimus is a substrate of the efflux transporter P-glycoprotein (Pgp) *in vitro*. If TORISEL® is administered with drugs that inhibit Pgp, increased concentrations of temsirolimus are likely, and caution should be exercised. *In vitro*, temsirolimus inhibited human Pgp (IC50 value of 2µM). If TORISEL® is administered with drugs that are substrates of Pgp, increased concentrations of the substrate drug are likely and caution should be exercised.

No dosage adjustment for temsirolimus is recommended in patients with renal impairment. There have been no clinical studies of this agent in patients with impaired renal function, though renal impairment is not expected to markedly influence drug exposure. Less than 5% of total radioactivity was excreted in the urine following a 25 mg intravenous dose of [14C]-labeled

temsirolimus in healthy subjects. Temsirolimus has not been studied in patients undergoing hemodialysis.

Temsirolimus is cleared predominantly by the liver.

Contraindications

Temsirolimus IV is contraindicated in persons with known hypersensitivity to temsirolimus or any component of the formulation. Temsirolimus is contraindicated in patients with bilirubin >1.5 x ULN.

Availability

Temsirolimus is FDA-approved for the treatment of advanced renal cell carcinoma (RCC). Temsirolimus will be supplied for this trial directly by the manufacturer, Pfizer, Inc., from commercial supplies. See *Section 4.2 Drug Accountability*.

Storage and handling

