5.3 Management of Toxicities

Each patient receiving at least 1 dose of temsirolimus in combination with at least 1 dose of sorafenib will be evaluable for safety. The safety parameters include all laboratory tests and hematological abnormalities, physical findings, and spontaneous reports of adverse events reported to the investigator by patients.

Each patient will be assessed periodically for the development of any toxicity as outlined in Table 6.1, Schedule of Study Procedures and Assessments. Toxicity will be assessed according to the NCI [CTCAE v4.0](#). Dose adjustments, treatment delay, and treatment discontinuation will be determined according to the system showing the greatest degree of toxicity. Toxicity will be formally assessed at protocol-defined assessment timepoints well as by investigator review of weekly laboratory testing and, in the interim, by patient contact with the study coordinator and/or treating investigator should new symptoms arise between visits. General principles of toxicity management are listed below:

- Temsirolimus and sorafenib will be dose-adjusted according to investigator's attribution of toxicity. In equivocal cases, the decision may be made by treating investigator.
- Asymptomatic changes in laboratory values require dose modification only if assessed to be treatment-related, clinically relevant, and represent a change of ≥ 2 grades from baseline.
- If toxicity occurs, supportive care medications should be applied to ameliorate signs and symptoms (including antiemetics for nausea and vomiting, antidiarrheals for diarrhea, antipyretics and antihistamines for drug fever, antihypertensives for hypertension, and phosphate repletion for hypophosphatemia) before toxicity grade is determined.

- A patient will be removed from protocol therapy if either of the two study drugs is discontinued.
- Temsirolimus will be discontinued if it is not tolerated at a dose of 5 mg IV weekly.
- Sorafenib will be discontinued if it is not tolerated at a dose of 200 mg PO every other day.
- Once a dose has been reduced for toxicity, it should not be re-escalated.
- In obese patients, all dosing is to be determined by the patient's actual body weight.
- If there is more than one indication for dose modification, use the more strict dose modification (i.e. modify according to the most severe toxicity).

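### Section 5.2.3: a recurrent Grade 2 bilirubin rise is released at Grade 2, so no recovery is required before temsirolimus restarts

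*Combined protocol and SAP*

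**What the plan says.** The bilirubin row at issue in section 5.2.3 is headed "Grade 2 (BILT > 1.5 to 3 times ULN". The cell gives the release grade for a first hold of both drugs, then the recurrence rule: "1, then decrease SOR by 1 DL and continue TEM at same dose; if recurs, hold both drugs and recheck weekly until ≤ Grade 2". After that second hold, temsirolimus drops one dose level and sorafenib continues unchanged. Grade 1 in the same block ends at 1.5 x ULN.

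Other text that bears on the point:

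- The Grade 3 bilirubin row: "Hold both drugs and recheck weekly until ≤ Grade 1, then decrease both drugs by 1 DL".
- The Grade 2 creatinine row, also > 1.5 to 3 x ULN: "if recurs, hold both drugs and recheck weekly until ≤ Grade 1, then decrease TEM by 1 DL and continue SOR at same dose".
- The Grade 3 transaminase and alkaline phosphatase row, directly below bilirubin, gives its first release grade and recurrence rule in the same form: "2, then decrease SOR by 1 DL and continue TEM at same dose; if recurs, hold both drugs and recheck weekly until ≤ Grade 2".
- Section 4.1.1, Contraindications: "Temsirolimus is contraindicated in patients with bilirubin >1.5 x ULN".
- Section 1.2.3, citing the prescribing information: "temsirolimus is contraindicated in patients with total bilirubin greater than 1.5 times the upper limit of normal".
- Section 5.3, on which laboratory changes count: "Asymptomatic changes in laboratory values require dose modification only if assessed to be treatment-related, clinically relevant", and only if the change is at least two grades from baseline.

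**The concern.** A hold with a release threshold is meant to keep the patient off drug until the toxicity has improved. Here the threshold for a second episode is set at the grade that triggered it, so it cannot do that. A patient whose bilirubin is unchanged at the weekly recheck, or has risen within Grade 2, qualifies to restart. In a first episode the same value would keep both drugs on hold.

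The matter is one of patient safety. Section 1.2.3 reports slower clearance, longer half-life and higher exposure to temsirolimus as hepatic function worsens, and cites the label limit of 1.5 x ULN. The trial admits Child-Pugh B patients with 7 points, and section 1.2.1.1 notes more hyperbilirubinemia on sorafenib in Child-Pugh B than in Child-Pugh A, so the situation is foreseeable. A site that follows the cell as written complies with the dosing table while re-dosing at a level the protocol elsewhere lists as contraindicated.

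**Working it through.** The plan gives no numerical result to reproduce here. The check compares ranges of bilirubin and then compares this row with the rest of the table.

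**Ranges.** Let b be bilirubin divided by ULN.

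- Trigger for the row (Grade 2): 1.5 < b ≤ 3.
- Release, first episode (≤ Grade 1): b ≤ 1.5.
- Release, recurrence (≤ Grade 2): b ≤ 3.
- Temsirolimus contraindication (sections 1.2.3 and 4.1.1): b > 1.5.

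*First episode.* Trigger and release ranges do not overlap, so bilirubin must fall before restart. Release and contraindication ranges do not overlap either.

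*Recurrence.* The trigger range (1.5, 3] lies wholly inside the release range b ≤ 3, so no fall is needed. The release and contraindication ranges overlap on (1.5, 3], which is the entire Grade 2 band.

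Ratio of release ceilings, recurrence to first episode: 3 / 1.5 = 2.

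**Comparison with the rest of section 5.2.3.** These are the rows that state a release grade for a recurrence:

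| Row | Trigger | First release | Recurrence release |
|---|---|---|---|
| Neutropenia | 3 | ≤ 2 | ≤ 2 |
| Thrombocytopenia | 3 | ≤ 2 | ≤ 2 |
| Nausea/vomiting, constipation, mucositis | 3 | ≤ 2 | ≤ 2 |
| Diarrhea | 3 | ≤ 2 | ≤ 2 |
| **Bilirubin** | **2** | **≤ 1** | **≤ 2** |
| Transaminase/alkaline phosphatase | 3 | ≤ 2 | ≤ 2 |
| Creatinine | 2 | ≤ 1 | ≤ 1 |
| Hypophosphatemia | 3 | ≤ 2 | ≤ 2 |
| Hand-foot syndrome | 2 | ≤ 1 | ≤ 1 |
| Other dermatologic | 2 | ≤ 1 | ≤ 1 |

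Nine of the ten release a recurrence below the trigger grade and at the same grade as the first episode. Bilirubin fails both tests and is the only row to fail either.

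The recurrence clause in the bilirubin row is identical to the one in the transaminase row beneath it. There the trigger is Grade 3, so ≤ Grade 2 is a real recovery. A copying slip is the likely explanation, but that is inference. The defect is the same whatever its cause.

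**After correction.** With the recurrence release at b ≤ 1.5, both overlaps within this cell vanish. The row then agrees with its own first-episode step, the Grade 3 bilirubin row and the Grade 2 creatinine row.

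**The case against.** The text of the cell is not in dispute. The case on the other side is about weight and reach.

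- *The contraindication is label information, not a study dosing rule.* Section 1.2.3 attributes it to the prescribing information, and section 4.1.1 is a drug description. If it binds sites, it already bars the restart and the two texts merely conflict. If it does not, what remains is an inconsistent release grade. Either reading leaves a contradiction in a safety table, and the missing recovery requirement does not depend on the contraindication.
- *The protocol allows temsirolimus above 1.5 x ULN by other routes.* Section 3.3.1 admits bilirubin up to 2 mg/dL as an alternative to 1.5 x ULN. If the local ULN were 1.0 to 1.3 mg/dL (an assumption; the documents give none), 2 mg/dL would be 2.0 to about 1.5 x ULN. Under section 5.3, an asymptomatic patient who starts at Grade 1 and rises to Grade 2 has moved one grade and needs no modification. This stands: correcting the cell does not close those routes. They are separate matters and do not justify the recurrence threshold.
- *Ascites is also lenient on recurrence.* New Grade 2 ascites is held until ≤ Grade 1 the first time, but a recurrence brings only a dose reduction. That is correct, and the count of ten covers only rows that state a recurrence release grade. Ascites states none.
- *Safeguards remain.* A hold is still ordered and may last until the next weekly recheck, temsirolimus falls one level, a recurrence at Grade 3 goes to the stricter row, and the investigator may delay longer or stop. All true, but discretion is optional and does not correct the threshold. The removal rule for irreversible toxicity in section 5.2.4 covers Grades 3 and 4 only.
- *Few patients will be affected.* Agreed; see the verdict.

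**Conclusion.** The concern holds. As written, a recurrence of Grade 2 hyperbilirubinemia can be released with no improvement, and temsirolimus can restart at up to 3 x ULN, twice the first-episode ceiling and inside the range the protocol itself calls contraindicated.

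The reach is narrow. It concerns patients who have one Grade 2 episode, recover to ≤ Grade 1, and then rise again but stay at Grade 2. For asymptomatic patients, section 5.3 further requires that the change be treatment-related, clinically relevant and at least two grades from baseline, which means a normal baseline bilirubin. The documents give no rate from which to estimate how many of the 25 to 28 patients this would be. The present text does not affect the definition of the primary endpoint, the sample size or the analysis. It should be corrected as a safety inconsistency; it does not undermine the trial's statistical design.

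The conclusion rests only on the grade definitions and release grades printed in section 5.2.3 and the contraindication in sections 1.2.3 and 4.1.1. It needs no outside figure.

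**What to change.** In the recurrence clause of the Grade 2 hyperbilirubinemia cell, replace ≤ Grade 2 with ≤ Grade 1. The Grade 2 creatinine row already has the wording: "if recurs, hold both drugs and recheck weekly until ≤ Grade 1, then decrease TEM by 1 DL and continue SOR at same dose".

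No new procedure is needed, since bilirubin is already measured weekly. The costs are:

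- Under section 10.4 the change is an amendment that needs approval by the Protocol Review Committee and the IRB before use.
- Some patients will be held longer. A hold for treatment-related toxicity beyond 28 days leads to removal under section 5.3, although the Study Chair may approve resumption in selected cases where the investigator sees clinical benefit.
- Removal for toxicity censors TTP, so the change could add a few censored observations. With so few patients likely to be affected, this is a small price for removing the contradiction.
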